[figure not shown]
[figure not shown]
[figure not shown]
[figure not shown]
[figure not shown]
[figure not shown]

## CLINICAL TRIAL PROTOCOL SYNOPSIS

Company name	Boehringer Ingelheim
Finished product name	Not applicable
Active ingredient name:	BI 655130
Protocol date	12 Sep 2018
Revision date	23 Oct2020
Trial number	1368-0008
Title of trial:	Mechanism of Action and Clinical Effect of BI 655130 in Patients with fistulizing Crohn's Disease
Principal Investigator < for single-centre trial or > Coordinating Investigator< for multi- centre trial if applicable >:	 Phone:  Fax: 
Trial site(s):	Multi-center trial
Clinical phase:	IIa
Objective(s):	

• To explore the pathomechanisms involved in the generation and healing of Crohn's Disease (CD) associated perianal fistulas

• To understand the mode-of-action (MoA) of BI 655130 in patients with CD and draining perianal fistulas

Methodology:	
Screening Cohort: is designed as a non-randomized screening cohort in patients with perianal fistulizing CD
 
Study Cohort: is designed as a randomized, double-blind and placebo-controlled, parallel-group phase IIa study of BI 655130

Number of patients entered:	Screening Cohort : Approximately 5 to 8 patients Study Cohort : Approximately 20 patients
Number of patients on each treatment:	Screening Cohort: not applicable Study Cohort: 
 
• Period 1: Approx. 10 patients per treatment arm (BI 655130 1200mg i.v. or placebo)
 
• Period 2: Treatment assignment in period 2 will be determined by the achievement of combined perianal fistula remission at week 12.
 

Diagnosis :	Patients with previously treatment-resistant perianal fistulizing CD with clinical indication for seton drainage
Main inclusion criteria:	
 
1. 18-75 years at date of signing informed consent
 
2. Diagnosis of clinical Crohn's Disease <math>\geq</math> 3 months prior to screening by clinical and endoscopic evidence and corroborated by a histopathology report
 
3. Has <math>\geq</math> 1 perianal active* fistula(s) with clinical indication for seton drainage (<math>\geq</math> 4 weeks duration before enrolment, as a complication of CD). **.           
 
* Criteria for Active Fistula: As per clinical evaluation: Presence of spontaneous drainage or drainage after gentle finger compression at the external openings & as confirmed by radiological (MRI) exploration .
 
** Patients who are screened with a seton drainage in place are eligible provided the drainage has not been in place for > 3 months and the patient meets the rest of the eligibility criteria
 
 
 
4. Additional enterocutaneous or abdominal fistulas are permitted (except rectovaginal fistulas)
 
5. Absent, mild or moderate clinical activity with CDAI <math>\leq</math> 250. CDAI is not applicable for Screening Cohort.
 
6. Demonstrated in the past inadequate fistula response or loss of response or have had unacceptable side effects with approved doses of at least one of the following compounds: Immunosuppressive agents (e.g. thiopurines, methotrexate), TNF<math>\alpha</math> antagonists (e.g. infliximab, adalimumab, certolizumab pegol; or respective biosimilars), vedolizumab, ustekinumab, azathioprine and / or antibiotics (cf. section 10.7)
 

Main exclusion criteria (Not applicable for Screening Cohort)	
 
1. Complications of Crohn's Disease such as symptomatic strictures, functional stenosis distal from fistula(s), short gut syndrome, or any other manifestation that might require surgery, could preclude the use of the PDAI and CDAI to assess response to therapy, or
 

	
would possibly confound the evaluation of benefit from treatment with BI 655130
 

2. Rectovaginal fistulas

3. Anticipated to require surgical intervention for CD, including any surgical fistula procedures (except seton drainage). See Table 4.2.2.2:1 for a detailed list of restricted interventions

4. Has an abscess that the investigator feels requires drainage beyond fistula drainage with a seton (based on either clinical assessment or MRI)

5. Any kind of bowel resection or diversion within 6 months or any other intraabdominal surgery within 3 months prior to screening.

6. Ileostomy, colostomy or known fixed symptomatic stenosis of the intestine at screening.

7. Evidence of colonic mucosal dysplasia or colonic adenomas, unless properly removed (properly according to the investigator's assessment)

8. Faecal Microbiota transplant (FMT) within 6 months prior to randomization

9. Treatment with: (See table 4.2.2.1:1 for a detailed list of restricted treatments)

• any non-biologic medication (incl. cyclosporine, JAK inhibitors such as tofacitinib, tacrolimus, sirolimus, mycophenolate mofetile, S1P modulators, SMAD7 antisense inhibitors such as mongersen), other than those allowed per chapter 4.2.1 within 30 days prior to randomisation unless these patients show an undetectable plasma concentration

• any biologic treatment approved for CD other than TNF<math>\alpha</math> inhibitors, within 8 weeks prior to randomization unless these patients show an undetectable plasma concentration

• any investigational or non-approved biologic for CD (including but not limited to IL-23 inhibitors) within 12 weeks prior to randomisation or etrolizumab within 8 weeks prior to randomization unless these patients show an undetectable plasma concentration

• rectal 5-ASA, rectal Tacrolimus, parenteral or rectal corticosteroids (incl. budesonide) within 2 weeks prior to randomisation

• any antibiotics within 1 week prior to randomisation

• any prior autologous or allogeneic, haematopoietic (HSC) or mesenchymal stem cell (MSC) therapy

• any prior exposure to BI 655130

• any chronic use of NSAID within 2 weeks prior to randomisation

--	---

	
(occasional use of NSAIDs and acetaminophen for headache, arthritis, myalgias, menstrual cramps, etc., and daily use of baby or low dose (81-162.5mg) aspirin for cardiovascular prophylaxis are permitted)
 
 
any life-attenuated vaccines within 6 weeks prior to randomization
 

Test product(s):	BI 655130 (Screening Cohort: not applicable)
dose:	
1200 mg every 4 weeks (q4w):
 
 
Period 1: at week 0, 4, 8
 
Period 2: at week 12, 16, 20
 

mode of administration:	Intravenous (i.v.)
Comparator products:	Placebo (Screening cohort: not applicable)
dose:	
0 mg (placebo) every 4 weeks (q4w):
 
 
Period 1: at week 0, 4, 8
 
Period 2: at week 12, 16, 20
 

mode of administration:	Intravenous (i.v.)
Duration of treatment:	
Screening Cohort: not applicable          Study Cohort: 24 weeks

Endpoints	
Primary endpoint:          The primary endpoint is the total number of deregulated genes at week 4 comparing changes in gene expression from baseline between the two treatment groups. Thereby, deregulation of a gene is defined based on the baseline adjusted mean difference to placebo of gene expression fulfilling the following criteria:
 
 
False discovery rate (FDR) adjusted p-value <math>\leq 0.05</math>
 
<math> \text{fold change}  \geq 1.5</math>
 
genes can be annotated with Ensembl identifiers (version 84 or later)
 
 
Gene expression is analysed based on biopsies (curettage and inner fistula orifice) via RNA sequencing; more details on the gene expression analysis can be found in Section 7.3.1
 
Secondary endpoints:
 
 
Proportion of patients with perianal fistula response at week 12 (defined as closure of at least 50% of external openings, no drainage / discharge despite gentle finger compression of fistulas that were draining at baseline and without new emerging fistulas)
 

	

• Proportion of patients with perianal fistula remission at week 12 (defined as closure of all external openings, no drainage / discharge despite gentle finger compression of fistulas that were draining at baseline and without new emerging fistulas)

• Proportion of patients with combined perianal fistula remission at week 12 (defined as closure of all external openings, no drainage / discharge despite gentle finger compression of fistulas that were draining at baseline and without new emerging fistulas, AND absence collections of >2 cm, confirmed by MRI in at least two of three dimensions – blinded and centrally read)

Safety criteria:	Physical examination, vital signs, 12-lead ECG, laboratory tests, adverse events, serious adverse events and drug-related adverse events. The intensity grading of AEs and abnormal laboratory values will be performed according to Rheumatology Common Toxicity Criteria (RCTC) Version 2.0
Statistical methods:	Gene expression analysis via repeated measures linear regression model (calculation of total number of deregulated genes at Week 4). Descriptive statistics for safety, [REDACTED] and efficacy endpoints. If feasible, 95% confidence intervals for rate difference in perianal fistula response, perianal fistula remission, and further clinical efficacy endpoints regarding proportions of patients.

## FLOW CHART A: SCREENING COHORT

Trial Periods	Screening Visit	Fistula Preparation Visit	Follow-up Visit
Visit	V1	V2	V3
Week	-4 to 0	0	3
Day	-28 to -1	1	21
Time window for visits (days)	n.a.		±7
Informed consent	X		
In-/exclusion criteria	X		
Demographics, Medical history incl. smoking, Crohn's Disease history, Prior therapies	X		
Physical examination (incl. vital signs) 1)	X C	X T	X T
Weight, Height 2)	X	X	X
Rectoscopy and Proctoscopy		X	
	X		X
Biopsy at the inner fistula orifice 3)		X	
Curettage at the fistula canal 3)		X	
Seton placement 3)		X	
Biopsy at the outer fistula orifice 3)		X	
Rectal luminal biopsy 3)		X	
Concomitant therapy	X	X	X
Adverse events	X	X	X

1) Physical examination: C=complete, T=targeted. Refer to [Section 5.2.1](#).  
 Vital signs: Measurement should precede blood sampling to avoid the impact of blood sampling on the vital measurements.

2) Height: To be done at screening visit 1, only.

3) Refer to [section 3.1](#) for requested tissue samples.

## FLOW CHART B: STUDY COHORT, PERIOD 1 (SCREENING – WEEK 8)

Trial Periods	Screening Period*			Randomized Treatment Period			
	Visit	V1a (Screening)	V1b (Pre-baseline)	V1c	V2 (Base-line)	V3	V4
Week	-5 to -3	-5 to -3	-3	0	2	4	8
Day	-35 to -22	-35 to -21	-21	1	15	29	57
Time window for visits (days)	n.a.	n.a.	+ 4	n.a.	± 4	± 4	± 4
Informed consent	X						
In-/exclusion criteria	X		X				
Demographics	X						
Medical history incl. smoking, Crohn's Disease history	X						
Prior therapies	X						
Physical examination (incl. vital signs) 1)	X C			X T	X T	X T	X T
Weight, Height 15)	X			X		X	X
Pregnancy Test 2)	X			X		X	X
[REDACTED]							
[REDACTED]			X			X	
Fistula preparation visit: 4) Biopsy at the inner fistula orifice Curettage at the fistula canal [REDACTED]			X			X	
Seton placement			X				
Seton removal						X	
[REDACTED]			X			X	
[REDACTED]			X Before Surgical Procedure			X	
[REDACTED]	D		X R Before Surgical Procedure	D	XR D	XR D	XR D
Imaging Pelvic MRI [REDACTED]			X  Before Surgical Procedure at V1c				
Concomitant therapy	X			X	X	X	X
Adverse events	X	X	X	X	X	X	X
12 lead-ECG	X			X			
Safety laboratory tests 6)	X			X	X	X	X
Infection testing 7)	X						

Flow Chart B: STUDY Cohort, Period 1 (Screening – Week 8) (cont.)

Trial Periods	Screening Period*			Randomized Treatment Period			
	V1a (Screening)	V1b (Pre-baseline)	V1c	V2 (Base-line)	V3	V4	V5
Week	-5 to -3	-5 to -3	-3	0	2	4	8
Day	-35 to -22	-35 to -21	-21	1	15	29	57
Time window for visits (days)	n.a.	n.a.	+ 4	n.a.	± 4	± 4	± 4
QuantIFERON-TB test	X						
[REDACTED]				■	■	■	■
[REDACTED]				X	X	X	X
[REDACTED]				X		X	X
[REDACTED]				■			
[REDACTED]				■		■	■
[REDACTED]				■		■	
[REDACTED]	X						
[REDACTED]				X			X
Contact IRT	X			X		X	X
Randomization				X			
Study drug administration				X 12,13		X 13, 14	X 13

\*) Once the gene expression analyses from the obtained fistula canal samples in the SCREENING COHORT have confirmed the eligibility criteria, enrolment of the STUDY COHORT will be initiated. Otherwise, the sponsor may decide to amend the study in order to obtain the relevant tissue from all study participants.

1) Physical examination: C=complete, T=targeted. Refer to [Section 5.2.1](#).

Vital signs: Measurement should precede blood sampling to avoid the impact of blood sampling on the vital measurements. In addition, at dosing visits vital signs will be assessed pre-dose, approximately 10 minutes and 1 hour after study drug administration.

Monitor for signs and symptoms of hypersensitivity reactions for approximately 2 hours after the first dose administered at Visit 2 and 1 hour following all other doses of study drug.

2) Only applicable for women of childbearing potential. A serum pregnancy test will be performed at screening. Urine pregnancy tests will be performed at all other visits indicated in the [Flow Chart](#). In case of a positive urine pregnancy test, a serum pregnancy test will be done. Urine pregnancy testing should be done prior to administration of study drug in case there is dosing at study visits. Study drug should only be administered in case of a negative test result.

4) Based on the outcome of the Screening Cohort it has been decided to keep the tissue sampling approach as initially planned. (cf. [section 3.1](#))

5) MRI

Decision on eligibility (exclude abscesses  $\geq 2$  cm, confirm fistula activity according to inclusion criterion 4) and progress of patients is based on assessment by investigator(s) on site.

Visit 1b: MRI results to be reviewed PRIOR to surgical procedures at visit 1c.

[REDACTED]

6) Includes parameters as listed in [Table 5.2.3:1](#) and [5.2.3:2](#).

It is preferred but patients do not have to be fasted for the blood sampling for the safety laboratory. At visits with study drug administration this should be done prior to the study drug infusion.

7) Infection Testing: See [section 5.2.3](#) safety laboratory parameters for complete list of testing required.

8) At study visits with study drug administration, pre-dose PK/ADA/nAb and biomarkers samples should be obtained within 1 hour prior to start of i.v. infusion.

9) If collection is not possible at Visit 1a, stool sample has to be collected at (or prior to) Visit 1c.

[REDACTED]

11) A diary will be used by the patient for the daily reporting of bowel movement frequency, abdominal pain and general

[REDACTED]

Refer to [Section 6.2](#).

12) First study drug will be administered at V2.

13) Patients who terminate study drug early should be encouraged to follow all study procedures per the [Flow Chart](#) until week 24, but not receive any more study drug at the respective visits. These patients do have the option to do EOS visit earlier than week 36 (their EOS visit should not be earlier than 16 weeks after their last study drug administration). Until then they should follow the [Flow Chart](#).

14) [Visit 4](#): I.v. administration and related procedures may be done within max. of 3 days after other investigations / procedures, if otherwise too difficult due to logistical reason.

15) Height: To be done at screening visit 1a, only.

[REDACTED]

[REDACTED]

**FLOW CHART C: STUDY COHORT, PERIOD 2 (WEEK 12 – WEEK 36)**

Trial Periods	Randomized Treatment Period				Follow-up Period
	V6 (treatment decision)	V7	V8	V9 / EOT	
Visit	V6 (treatment decision)	V7	V8	V9 / EOT	V10 / EOS 11)
Week	12	16	20	24	36
Day	85	113	141	169	253
Time window for visits (days)	± 4	± 4	± 4	+7	+7
Physical examination (incl. vital signs) 1)	X C	X T	X T	X C	X C
Weight	X	X	X	X	X
Pregnancy Test 2)	X	X	X	X	X
[REDACTED]	[REDACTED]			[REDACTED]	
[REDACTED]	X			X	
[REDACTED]	X			X	
[REDACTED]	X 4)			X	
[REDACTED]					
[REDACTED]	XR D	XR D	XR D	XR D	XR
Imaging: Pelvic MRI [REDACTED]	X 5)			X	
Concomitant therapy	X	X	X	X	X
Adverse events	X	X	X	X	X
12 lead-ECG	X			X	X
Safety laboratory tests 6)	X	X	X	X	X
QuantiFERON-TB test				X	
[REDACTED]	X	X	X	X	X
[REDACTED]	X		X	X	X
[REDACTED]	X	X	X	X	
[REDACTED]	X	X	X	X	

Flow Chart C: Study Cohort, Period 2 (Week 12 – Week 36) (cont.)

Trial Periods	Randomized Treatment Period				Follow-up Period
	V6 (treatment decision)	V7	V8	V9 / EOT	
Visit	V6 (treatment decision)	V7	V8	V9 / EOT	V10 / EOS 12)
Week	12	16	20	24	36
Day	85	113	141	169	253
Time window for visits (days)	± 4	± 4	± 4	+7	+7
Stool sampling for microbiome and miRNA analysis	X			X	
[REDACTED]	X			X	
Contact IRT	X 12)	X 12)	X 12)	X	
Study drug administration	X 4) 10), 11)	X 4) 10)	X 4) 10)		
Study completion 12)				X	X
Roll-over into 1368-0007 12)				X 12)	

1) Physical examination: C=complete, T=targeted. Refer to [Section 5.2.1](#).

**Vital signs:** Measurement should precede blood sampling to avoid the impact of blood sampling on the vital measurements. In addition, at dosing visits vital signs will be assessed pre-dose, at approximately 10 minutes and 1 hour after study drug administration.

Monitor for signs and symptoms of hypersensitivity reactions for approximately 2 hours after the first dose administered at Visit 2 and 1 hour following all other doses of study drug.

2) Only applicable for women of childbearing potential. A serum pregnancy test will be performed at screening. Urine pregnancy tests will be performed at all other visits indicated in the [Flow Chart](#). In case of a positive urine pregnancy test, a serum pregnancy test will be done. Urine pregnancy testing should be done prior to administration of study drug in case there is dosing at study visits. Study drug should only be administered in case of a negative test result.

4) Perianal fistula activity at week 12: Refer to chapter [3.1](#) and [5.1.2](#)

Treatment assignment in period 2 will be determined by the achievement of combined perianal fistula remission at week 12 based on assessment by investigator(s) on site.

- Combined perianal fistula remission = yes: stay on current drug
- Combined perianal fistula remission = no: switch to active drug if treated with placebo in period 1  
 proceed with active drug if treated with active drug already in period 1

5) MRI

Visit 6:

MRI to be performed in a time window of 2 weeks PRIOR to visit 6. MRI result to be available at visit 6 for the evaluation of combined perianal fistula remission performed by investigator(s) on site.

6) Includes parameters as listed in [Table 5.2.3:1](#) and [5.2.3:2](#).

It is preferred but patients do not have to be fasted for the blood sampling for the safety laboratory. At visits with study drug administration this should be done prior to the study drug infusion.

[REDACTED]

10) Patients who terminate study drug early should be encouraged to follow all study procedures per the [Flow Chart](#) until week 24, but not receive any more study drug at the respective visits. These patients do have the option to do EOS visit earlier than week 36 (their EOS visit should not be earlier than 16 weeks after their last study drug administration). Until then they should follow the Flow Chart.

11) Visit 6: I.v. administration and related procedures may be done within max. of 3 days after other investigations / procedures, if otherwise too difficult due to logistical reason

12) All patients completing week 24 of the study and having an individual clinical benefit may be offered to enter open label long-term extension study 1368-0007. These patients are not requested to complete follow up period and the visit 09 is the last visit for trial 1368-0008, probably co-inciding with the first visit in 1368-0007. For AE and Concomitant therapy reporting the end of study participation is defined as the day of first administration of study drug in 1368-0007.

[REDACTED]

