Figure 3.1:3 schematic overview treatment decision responders

- Patients *without combined perianal fistula remission* (irrespective of period 1 treatment) will be treated with BI 655130 1200 mg i.v. every 4 weeks (week 12, week 16 and week 20) as shown in [figure 3.1:4](#). Such patients originally assigned to placebo will thus switch to active drug.

[figure not shown]

Figure 3.1:4 schematic overview treatment decision non-responders

Follow-up period:

Patients who terminate study drug early or do not enrol into the subsequent long-term extension study 1368-0007, will continue safety follow up until 16 weeks after last study drug

administration. These patients, who drop out of the study, will receive standard of care treatment per investigator's discretion.

*Patients who complete the EOT visit* (visit 9, week 24) in period 2 of this study and who have individual clinical benefit may enter the long-term extension study 1368-0007, which offers open label active treatment with subcutaneous BI 655130.

Background therapy for underlying CD with conventional immunosuppressants or anti-TNF  $\alpha$  compounds (provided that is allowed (cf. [section 4.2.1](#))).

Individual patient participation is concluded when the patient has completed the last planned visit.

The end of the trial is defined as "last patient out", i.e. last scheduled visit completed by last patient.

An interim analysis of the Study Cohort is planned, please refer to [section 7.4](#)

An overview of all relevant trial activities is provided in the [Flow Chart](#). For visit schedules and details of trial procedures at selected visits, refer to [Section 6.1](#) and [Section 6.2](#), respectively.

Table 3.1:1 Study definitions

Rescue Medication	New or increase in dose of any medication applied to treat new or persisting symptoms related to CD
Disease worsening	Worsening of clinical status or symptoms of CD requiring administration of rescue medication in the investigator's opinion – in patients without a clinical response

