The double blind and placebo controlled induction period 1 of the *Study Cohort* allows to compare gene and biomarker expression in patients with perianal fistulizing CD under conditions of placebo treatment or IL36R inhibition. The results will be critical to longitudinally characterize the mechanisms of disease involved in the evolution of fistulas, and assess the MoA in the active treatment group. The short period of placebo treatment is justified due to the previous failure of the selected patients to approved standard of care treatments, the subsequent cross-over to double blind treatment with active drug in case there is no perianal fistula remission at week 12, and the expected group benefit for patients with perianal fistulizing CD resulting from an improved understanding of the pathophysiology of this disease and the MoA of a new treatment candidate. The placebo group will also serve as appropriate comparator to investigate clinical effect size and safety/tolerability of BI 655130 in this disease. Placebo patients not achieving a strictly defined combined perianal fistula remission (which is unlikely to occur on PBO) will be switched to active drug. Patients experiencing disease worsening during the treatment period can be discontinued from treatment at any time at the investigator's discretion. Responders to induction treatment, in contrast, are expected to benefit from maintenance treatment, e.g. by the achievement of luminal and/or fistula remission or mucosal healing, and by prevention of relapses. All patients completing the 24 weeks course of the study with an individually perceived clinical benefit will be offered to roll-over into an open label long-term study offering continued BI 655130 treatment for up to additional 7 years.

Since a PoC for BI 655130 is not yet available in CD, the chance of an individual benefit for study participants is difficult to estimate, and thus sample size and treatment duration were limited to a minimum and based on practical feasibility to achieve the study objectives.

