##### Study Cohort, Period 2: Double blind

Treatment in period 2 starting in visit 6 (BI 655130 1200mg i.v. every 4 weeks or placebo) will be determined by the outcome at week 12 (cf. [section 3.1](#)). The assignment will occur in a blinded fashion via Interactive Response Technology (IRT).

Details regarding the use of the IRT are described in the site-user manual available in the ISF.

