#### 4.1.5 Blinding and procedures for unblinding

##### 4.1.5.1 Blinding

###### Study Cohort, Period 1 and 2: Double blind

Patients and investigators (including the research staff at the trial site) will remain blinded with regard to the randomized treatment assignments until the final database lock for the final trial analysis.

The interim analysis, which is the primary analysis of the trial will be performed once all randomized patients have completed through 12 weeks of trial treatment. At this time, a preliminary database lock will be done and treatment will be unblinded. In order to confirm the integrity of the treatment blind while the trial continues through to completion, a logistics plan will be developed to describe the mechanisms that are to be put in place to assure that

the patients and investigators remain blinded to both individual patient data, as well to the primary analysis results. The blind status of trial and project team members at this time will also be clarified. The logistics plan will be finalized prior to the treatment unblind for the primary analysis.

The randomization code will be kept secret by Clinical Trial Support and will not be accessible prior to the preliminary database lock for the interim analysis by anyone else involved in the trial with two exceptions. The bioanalytical laboratory will receive the randomization code during the trial conduct in order to avoid testing of placebo patient samples for PK and ADA. The bioanalytical laboratory can be regarded as totally independent from the trial team. After the last patient completes the Week 12 visit the random plan will be released to the bioinformatics group. The bioinformatics group will receive the randomisation code in order to start with the pre-processing of gene expression data (using limma packages).

Bioinformatics groups and the analytical laboratory will not disclose the randomization code until the trial is officially unblinded.

A fully external DMC will perform an un-blinded safety and efficacy assessment at specified intervals in order to ensure that patients are protected from potential harm, please refer to [Section 7.4](#) for further details.

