#### Study Cohort:

At dosing visits vital signs evaluations will be performed *pre-dose* and additional evaluation will be taken at approximately *10 minutes and 1 hour post-dose*.

Monitoring for hypersensitivity reactions:

Patients should be closely monitored for signs and symptoms of hypersensitivity reactions for approximately *2 hours* after the *first dose* administered at visit 2 and *1 hour* following all *other doses* of study drug. Hypersensitivity reactions should be treated according to medical standards. Pre-medications for further infusions might be considered and will be agreed on between investigator and BI clinical monitor.

The investigator should evaluate the clinical significance of the results. Clinically abnormal findings will be reported as baseline condition or AEs.

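### The 2-hour hypersensitivity observation is tied to Visit 2, so the protocol's required minimum after a switched placebo patient's first spesolimab infusion is 1 hour

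*Protocol*

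**What the plan says.** Footnote 1 of Flow Chart C, which covers Visits 6 to 10, sets the observation period at "approximately 2 hours after the first dose administered at Visit 2 and 1 hour following all other doses of study drug". Footnote 1 of Flow Chart B has the same rule for period 1. Section 5.2.2 repeats it for the Study Cohort ("Patients should be closely monitored for signs and symptoms of hypersensitivity reactions for approximately" 2 hours, again naming visit 2, and 1 hour for the other doses). Post-dose vital signs at dosing visits are scheduled at about 10 minutes and 1 hour.

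On treatment in period 2, Flow Chart C footnote 4 says that patients without combined perianal fistula remission at week 12 "switch to active drug if treated with placebo in period 1". Section 3.1 confirms this: "Such patients originally assigned to placebo will thus switch to active drug". Those already on spesolimab continue it, and remitters stay on whatever they had. Prior exposure to BI 655130 is prohibited (exclusion criterion 10 and Table 4.2.2.1:1).

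On blinding, section 4.1.5.1 states: "Patients and investigators (including the research staff at the trial site) will remain blinded with regard to the randomized treatment assignments". The period 2 assignment is made blind through the IRT (section 4.1.3). The week-12 remission decision that drives it is made by the investigator on site (Flow Chart C footnote 4, section 5.1.2).

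**The concern.** A longer watch after a first dose makes sense if the first exposure to the antibody is the moment that calls for most care. The sponsor has adopted that precaution, and infusion reactions including anaphylaxis are an adverse event of special interest (section 5.2.6.1). By naming Visit 2, however, the rule attaches the precaution to the first infusion of study drug, which for half the patients is placebo. A placebo patient who switches has the 2-hour watch after an inactive infusion and the repeat-dose minimum after the first active one. Flow Chart C is where an exception for Visit 6 would be expected, and it repeats the Visit 2 wording unchanged.

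At stake is equal application of the sponsor's own first-dose precaution to both randomised arms. The primary and secondary endpoints are not involved.

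**Working it through.** The plan gives no figure to reproduce. The check applies the observation rule to each dosing visit and finds the period that follows the first active infusion.

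Inputs:
- Dosing visits: V2, V4 and V5 in period 1 (weeks 0, 4, 8); V6, V7 and V8 in period 2 (weeks 12, 16, 20). Source: Flow Charts B and C.
- Observation: about 2 hours at V2, 1 hour at all other doses. Source: footnote 1 of both flow charts, section 5.2.2.
- Treatment sequences: Pbo-Pbo, Pbo-Speso, Speso-Speso. Source: SAP section 6.1.
- Arm size: about 10 patients each, about 20 in total. Source: protocol synopsis.

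| Sequence | First active infusion | Required observation after it |
|---|---|---|
| Speso-Speso | V2 | about 2 hours |
| Pbo-Speso | V6 | 1 hour |
| Pbo-Pbo | none | not applicable (2 hours follow placebo at V2) |

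Because the rule names the visit, a Visit 6 infusion can only fall under the other doses. Because prior exposure is prohibited, Visit 6 is a true first exposure for every patient in the Pbo-Speso row, provided that the Visit 6 dose is given. If it is missed, the first active dose comes later and is still covered by the 1-hour rule.

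Number affected = placebo patients − placebo patients in combined remission at week 12 − placebo patients off drug by then. The documents give no rate for either subtraction. They say only that combined remission is something "which is unlikely to occur on PBO".
- Upper bound, with no remitters and no discontinuations: 10 − 0 − 0 = 10.
- Illustration, assuming that 1 or 2 of 10 remit and none stop: 10 − 1 = 9, or 10 − 2 = 8.

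At the upper bound, the 10 switched patients supply 10 / (10 + 10) = 50% of all first spesolimab infusions in the trial.

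Whether a correction threatens the blind can be settled from the allocation rule. At week 12 the site knows who is a non-remitter, and every non-remitter receives spesolimab in period 2 whatever was given in period 1. What the site does not know is which non-remitters had placebo before. A 2-hour period for all non-remitters would treat Pbo-Speso and Speso-Speso non-remitters alike, so length of stay would reveal only remission status, which the site already has. A rule for all patients reveals nothing either.

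**The case against.** The strongest reply is that the text sets a minimum. It says approximately and should, gives no maximum, and leaves an investigator free to keep a patient longer. Section 1.4 refers infusion-reaction monitoring to the handling instructions for BI 655130, and sections 4.1.4 and 4.2.1 place further instructions in the ISF. Those papers were not available for review and could set a longer period at Visit 6. This stands. A reader might infer that switched patients will actually be watched for only 1 hour; the documents support only that 1 hour is what the protocol requires.

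A reader might also infer that blinded sites have no way to compensate. That does not follow. Sites cannot identify who switched, but they know that each non-remitter receives active drug at Visit 6, possibly for the first time, and can observe all of them longer without unblinding. For the same reason, extending the rule to every patient is a convenience and not a condition for keeping the blind.

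The risk is unquantified. Nothing in the documents shows excess risk in the second hour, and section 1.4 says that infusion reactions were not an issue in phase I. Section 1.2.3 does report one suspected infusion reaction of moderate intensity that led to withdrawal of study drug, in the 20 mg/kg multiple-dose cohort. It was a single event under a different regimen with no timing given, so it makes the precaution reasonable but does not show a hazard between 1 and 2 hours.

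Finally, a reader might extend the point to the COVID-19 clause in section 4.1.4, which allows trial medication to be shipped to a patient's home. That route needs a benefit-risk assessment, discussion with the sponsor and local legality, and nothing shows that a first active infusion would be given that way. No change to section 4.1.4 is needed on this account.

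What the reply leaves untouched is the asymmetry in the protocol text: three statements of the rule, none with an exception at Visit 6.

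**Conclusion.** The point holds as a gap in the protocol's required minimum. For up to about 10 patients, the first spesolimab infusion carries a required observation of 1 hour, against about 2 hours for patients randomised to spesolimab. The figure of 10 is an upper bound that assumes the planned arm size, no combined remission on placebo and no early discontinuation.

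The conclusion rests on the protocol and SAP alone. If the ISF instructions already set 2 hours at Visit 6, practice may be adequate, but the protocol would still direct a shorter period and should be brought into line. The change is a low-cost precaution. It does not bear on the primary or secondary endpoints or their analysis.

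**What to change.** In Flow Chart B footnote 1, Flow Chart C footnote 1 and section 5.2.2, require about 2 hours of observation after the Visit 2 dose and after the first dose given on or after Visit 6, and 1 hour after all other doses. Wording it as on or after Visit 6 matches the start of period 2 in SAP Table 6.1: 1 and covers a missed Visit 6 dose.

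Applying it to all patients is simplest. Applying it to all week-12 non-remitters is enough, since remitters never have a first active dose in period 2. Align the ISF handling instructions if they differ.

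The cost is one clause in three places, with no new procedure. For all patients, the extra time is at most 20 patients × 1 hour = 20 patient-hours over the trial. It is less if only non-remitters are covered or if some patients are off drug by Visit 6.
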